4.5. Protocol Alterations

Protocol alterations are alternative methods of assessments due to the COVID-19 pandemic. For subjects who could not attend clinic visits due to the pandemic, protocol alterations in place for this study are home visits or telephone assessments. A listing of subjects with protocol alterations will be provided.

4.6. Study Treatment Exposure

Summaries for extent of exposure to study treatment will be summarized for the overall safety population by study group.

A frequency distribution for number of doses received per subject will be summarized by study group, and descriptive statistics will be presented for total cumulative dose during 233AS102 in mg. Total cumulative dose will be based on actual dose administered (calculated as volume administered multiplied by dose, and divided by 15mL). For Part A/B subjects the frequency distribution for number of doses received per subject will also be broken down by <100 mg and 100 mg.

A delayed visit or dose will be anything that falls outside of the following protocol-defined windows of +/-3 days

The following summaries will be presented by study group:

- Total number of expected doses across subjects based on actual subject duration of dosing; total number of missed doses and total number of delayed doses (percentages calculated out of total number of expected doses);
- A frequency distribution for number of consecutive missed doses per subject. If a subject has more than one period where doses were missed consecutively, the period with the maximum consecutive missed doses will be used;
- A frequency distribution for overall number of missed doses per subject (i.e. regardless of whether they were consecutive). The mean (SD) will be presented for the mean number of missed doses per subject. Subjects with no missed doses will be included as having 0 missed doses.
- The mean (SD) number of delayed doses per subject will also be summarized. Subjects with no delayed doses will be included as having 0 delayed doses. A delayed dose is based on regular scheduled visits, as dosing cannot be recorded under unscheduled visits.

The summaries described above for missed and delayed doses will be repeated based on doses that are missed or delayed due to COVID-19 impact.

A listing will also be presented to show dosing history for all subjects who missed at least one dose, indicating whether any of the missed doses are related to COVID-19. If any of the doses are due to COVID-19, then the number of impacted doses will be presented.

Study drug compliance percentage up to the last dose of study drug received will be defined as the number of doses actually received divided by the number of doses that the subject is expected to receive during the study period and will be summarized by descriptive statistics. For subjects who withdrew from study early, the number of expected doses is the planned number of doses before the time of withdrawal.

Study drug administration data will be listed which will include lot numbers, dose received, cumulative number of doses and cumulative dose. A listing of dosing errors will also be provided

i.e. where either the incorrect dose was administered as specified in protocol deviation log and kit description from IRT system. Actual dose will be calculated as volume administered multiplied by dose and divided by 15mL. The nominal dose will also be presented.

Time on study will be summarized descriptively by study group. Overall time on study will be calculated as last date on study at time of cutoff – first dose date + 1 in days. Last date on study is defined as the date of the latest visit or evaluation or telephone contact, or time of death from all available data for a given subject. The durations will also be categorized and summarized using 12-week intervals the following categories: ≤12 weeks, >12 weeks to 24 weeks, >24 weeks to 36 weeks, >36 weeks to 48 weeks, >48 weeks to 60 weeks, >60 weeks to 72 weeks, >72 weeks to 84 weeks, and so on.

A summary of time to treatment discontinuation will be provided for those subjects who discontinued study drug, calculated as last dose date – first dose date +1.

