7.2. Overall Study Duration and Follow-Up

The overall duration of study participation for a single participant will be up to 368 weeks, which includes an approximately 4-week screening period, up to a 360-week treatment period, and a 4-week follow-up period.

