7.4. End of Study

The end of study is last participant, last visit (approximately 4 weeks after their last dose). The last Maintenance Dose Visit for a participant will occur when the last participant enrolled has had the opportunity to have their Week 152 Maintenance Dose Visit.

CONFIDENTIAL

The information contained herein may not be used, disclosed, or published without the written consent of Biogen MA Inc.

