10. DISCONTINUATION OF STUDY TREATMENT OR WITHDRAWAL OF PARTICIPANTS FROM THE STUDY

10.1. Discontinuation of Study Treatment

A participant must discontinue study treatment for any of the following reasons:

- The participant becomes pregnant. Study treatment must be discontinued immediately. Report the pregnancy according to the instructions in Section [15.4.1](#).
- The participant withdraws consent to continue study treatment.
- The participant experiences a medical emergency that necessitates permanent discontinuation of study treatment.
- The participant is unwilling or unable to comply with the protocol.
- At the discretion of the Investigator or Sponsor.

The reason for discontinuation of study treatment must be recorded in the participant's CRF.

Participants who discontinue study treatment will be encouraged to remain in the study and complete all applicable protocol-specified tests and assessments. In circumstances when onsite visits are not possible, these assessments may be conducted by telephone.

Participants who terminate from the study early (i.e., discontinue both study treatment and study assessments) should complete the Final or Early Termination Visit. Home assessments will be allowed with Investigator approval for participants who are unable to complete the Final or Early Termination Visit at the site.

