21. SIGNED AGREEMENT OF THE STUDY PROTOCOL

I have read the foregoing protocol, "An Extension Study to Assess the Long-Term Safety, Tolerability, Pharmacokinetics, and Effect on Disease Progression of BIIB067 Administered to Previously Treated Adults with Amyotrophic Lateral Sclerosis Caused by Superoxide Dismutase 1 Mutation," and agree to conduct the study according to the protocol and the applicable ICH guidelines and GCP regulations, and to inform all who assist me in the conduct of this study of their responsibilities and obligations.

Investigator's Signature

Date

Investigator's Name (Print)

Study Site (Print)

CONFIDENTIAL

The information contained herein may not be used, disclosed, or published without the written consent of
Biogen MA Inc.

Biogen MA Inc.
[name]
Cambridge, MA 02142
United States

Biogen Idec Research Limited
[name]
[name]
Maidenhead, Berkshire
SL6 4AY
United Kingdom

AMENDMENT SUMMARY

Biogen Protocol 233AS102

An Extension Study to Assess the Long-Term Safety, Tolerability, Pharmacokinetics, and Effect
on Disease Progression of BIIB067 Administered to Previously Treated Adults with
Amyotrophic Lateral Sclerosis Caused by Superoxide Dismutase 1 Mutation

Version 6

Date: 04 August 2021

EUDRA CT Number: 2016-003225-41

Version 6 of the protocol has been prepared for this amendment, which supersedes Version 5.

CONFIDENTIAL

The information contained herein may not be used, disclosed, or published without the written consent of
Biogen MA Inc.

PRIMARY REASON FOR AMENDMENT

The primary reason for this amendment to Protocol 233AS102 is to extend the maintenance dosing portion of the treatment period of the study by up to 124 weeks while minimizing the burden on participants. Maintenance dosing will continue for all participants until the LPI has had the opportunity to reach Week 152 of the maintenance dosing period, which for the first participant in is Week 360. The maintenance dosing period will be followed by a Final Visit at 4 weeks after the last dose. This extends the study until the LPI reaches Week 156. Changes to the study visits include the following:

- The Follow-Up Visits before the Final/Early Termination visit will be eliminated.
- The Final or Early Termination Visit will now be held 4 weeks after the last dose.
- SVC and HHD will be completed every 12 weeks instead of every 4 weeks during the maintenance dosing period.

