2.3. Protocol Amendments

During the course of study conduct, protocol amendments were developed for Study 233AS102. Due to the changes of the assessments (e.g. adding assessments to align with Study 233AS101 amendment, removing assessments to minimize burdens on the subjects, changes of assessment frequency, etc.), the collected assessments and frequency may vary among subjects enrolled from Part A/B and Part C. Part C subjects started enrolling in Study 233AS102 at protocol amendment V4.0, thus the assessments changes in protocol amendment V4.0 or prior will have no impact on Part C subjects. The new assessments introduced in protocol amendment 4.0 or later (i.e. ventilation use, [REDACTED]) will only be collected part of the way through the study for Parts A and B subjects. [Table 2](#) below summarized the changes for the impacted endpoints.

MMSE was removed from the protocol amendment V6.0; however, we will include summaries for all the data collected.

Table 2: Summary of changes in protocol amendments

Endpoint	V3.0	V4.0	V5.0	V6.0
Neurological examination (excluding MMSE)	Changed to limited neurological examination (cranial nerves, coordination/cerebellar function, reflexes, motor)	Added post-dose timepoints	Removed cranial nerves examination	Removed from all dosing visits (except for pre-dose baseline)
MMSE		Added post-dose timepoints	Reduced from every 4 weeks to every 12 weeks prior to week 48, and to every 24 weeks up to week 216.	Removed
ECG				Removed from all dosing visits (except for pre-dose baseline)
Vital sign		Added post-dose timepoints		
Immunogenicity, PK		Decreased from 4 weeks to 8 weeks		
ALSFRS-R		Added Day 15		

SVC				Reduced from every 4 weeks to every 12 weeks
HHD		Added Day 15		Reduced from every 4 weeks to every 12 weeks
Ventilation use, [REDACTED]		Added		

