3.2. Study Group

Study participants will be assigned to one of the following study groups based on which part they enrolled from in 233AS101. All outputs will be presented using these groups unless otherwise specified:

Table 6 Study Groups of 233AS102

233AS101 Part C subjects by prior treatment	233AS101 Part A+ Part B subjects	233AS101 Part A, B and C subjects
placebo	tofersen 100 mg	All doses
		Total
This includes data from 233AS102 for subjects who received placebo in 233AS101 Part C during the randomized part of the study	This includes data from 233AS102 for subjects who received tofersen in 233AS101 Part C during the randomized part of the study	Subjects enrolled from 233AS101 Part A or 233AS101 Part B regardless of dose
		All subjects in 233AS102 i.e. addition of all 3 columns

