3.3.2.2 Maintenance Dose Period

During the maintenance portion of the study, subjects will receive up to 90 doses of tofersen, approximately every 4 weeks, during visits at Weeks 8, 12, 16, and every 4 weeks thereafter until the last subject enrolled has had the opportunity to have their Week 152 Maintenance Dose Visit.

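### Time to treatment discontinuation is summarised only among subjects who discontinued, so comparing A+B with Part C partly reflects length of potential follow-up; one censored summary would remove that

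*SAP*

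**What the plan says.** SAP section 4.6 (Study Treatment Exposure) plans this output: "A summary of time to treatment discontinuation will be provided for those subjects who discontinued study drug". The duration is last dose date minus first dose date plus one day. No censoring rule is given. The sentence names no columns, so the default in SAP section 3.2 applies: "All outputs will be presented using these groups unless otherwise specified". Those groups (Table 6) are Part C prior placebo, Part C prior tofersen, Parts A and B combined (A+B), and Total.

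Maintenance dosing continues "until the last subject enrolled has had the opportunity to have their Week 152 Maintenance Dose Visit" (SAP 3.3.2.2), and Protocol 7.4 ends a participant's dosing "when the last participant enrolled has had the opportunity to have their Week 152 Maintenance Dose Visit". Protocol 7.2 allows "up to a 360-week treatment period". The Version 6 amendment summary explains whose maximum that is: "which for the first participant in is Week 360". SAP 2.3 adds: "Part C subjects started enrolling in Study 233AS102 at protocol amendment V4.0".

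Other planned outputs touch on persistence:
- number and percentage discontinued, with reasons (SAP 4.2);
- number of doses received and cumulative dose by group (SAP 4.6);
- time on study for everyone in 12-week bands, measured to last contact or death (SAP 4.6).

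**The concern.** A mean or median taken only over people who stopped is bounded by how long each could have been observed. Two groups with the same discontinuation rate will show different values if one could be followed for longer. Here dosing ends for everyone at a common point, so potential dosing time depends on entry date. The first participant in must have come from Part A or B, because Part C entry began only at protocol Version 4. A+B therefore includes the longest potential follow-up, and Table 6 sets it beside Part C.

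SAP section 1 says the final standalone analyses will concentrate on safety and exposure, and tolerability is part of the primary objective. A reader of the study report may well ask how long participants stayed on drug in each group. As planned, no figure answers that with allowance for follow-up. The SAP does give adverse events follow-up-adjusted and exposure-adjusted rates (4.9.1), but gives discontinuation neither.

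**Working it through.** The documents state no time-to-discontinuation figure, so there is nothing to reproduce. The check asks how far the planned figure would move from follow-up alone.

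**Inputs from the documents.** Potential dosing time is about 152 weeks for the last entrant and 360 for the first.

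**Where Part C may top out.** Group entry dates are not given. The footnote to SAP Table 4 offers a rough anchor. For the earlier 4-weekly MMSE schedule, it applies 4-weekly windows up to Week 24 for Part C and Week 120 for A/B. This suggests that the first Part C entrant was about 120 − 24 = 96 weeks behind the first A/B entrant. Part C potential follow-up would then reach about 360 − 96 = 264 weeks. I use 264 to 270.

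**Assumptions.** Potential follow-up F is uniform within each group. The discontinuation hazard h is constant and, unless stated, equal in both groups. Weeks are divided by 52.18 to give years.

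**Formulas.**
- Proportion discontinued = E[1 − exp(−hF)].
- Mean time among discontinuers = E[(1 − exp(−hF))/h − F·exp(−hF)] / E[1 − exp(−hF)].

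**One fixed F, to show the mechanism.** With h = 0.15 and F = 152/52.18 = 2.913 years, exp(−hF) = 0.646. The mean is 1/0.15 − 2.913 × 0.646/0.354 = 1.35 years. The same formula gives 2.21 years at F = 264 weeks and 2.86 years at F = 360 weeks, with the rate unchanged.

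**Group results, ratio of means, A+B over Part C:**

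| Hazard per year | Overlapping entry (Part C 152–270, A+B 180–360 weeks) | Clean split at 264 weeks |
|---|---|---|
| 0.05 | 1.28 | 1.45 |
| 0.15 | 1.24 (1.84 and 2.29 years) | 1.40 (1.82 and 2.56 years) |
| 0.40 | 1.16 | 1.28 |
| 0.69 | 1.09 | 1.15 |
| 1.0 | 1.04 | 1.07 |
| Part C 0.15, A+B 0.30 | 1.05 | 1.18 |

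A clean split at 270 weeks also gives 1.40 at 0.15 per year. In the overlap case, Weibull hazards of shape 0.7 or 1.3, matched to the same 3-year discontinuation as 0.15 per year, give 1.25 and 1.23. The result does not depend much on a constant hazard.

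**What the n (%) table would show.** At an equal 0.15 per year it reads 45% in Part C against 53% (overlap) or 59% (split) in A+B, again from follow-up alone.

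**What a common time point would show.** Cumulative discontinuation at Week 152 is 1 − exp(−0.15 × 152/52.18) = 35% in both groups. At Weeks 52 and 104 it is 14% and 26%.

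**The case against.** The case for leaving the plan alone has four parts.

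- **The sentence is open about its scope.** It conditions on discontinuation and promises no between-group comparison. Protocol 16.1 says Part C will generally be analysed separately from Parts A and B, and SAP section 1 warns that A/B data are hard to interpret. This stands, and it is why the point is minor. The Table 6 default nevertheless sets the columns side by side.
- **Other outputs carry much of the information.** Doses received and cumulative dose cover the whole safety population. Week 152 corresponds to 3 loading plus (152 − 8)/4 + 1 = 37 maintenance injections, 40 in all. Because every participant is meant to have the opportunity to reach Week 152, the proportion stopping earlier is close to a simple count. This also stands: the data exist, and what is missing is a tabulation at a common time. As planned, none of these outputs is adjusted for follow-up, and time on study runs past the last dose.
- **The distortion may be small.** SAP section 1 reports a large proportion of discontinuations among A/B subjects across the studies. If A+B discontinues at twice the Part C rate, the ratio falls to 1.05 to 1.18. This stands too.
- **Censoring would not make the groups comparable.** Washout, dose history and disease stage still differ. This is correct, and the fix should not claim otherwise.

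A reader might also infer more than the documents support. One inference is that no two columns can be compared. The two Part C columns come from one randomised study, so their potential follow-up should be similar. Another is to give every Part C subject 152 weeks and every A+B subject 360. With a true median of 200 weeks, that would put the discontinuers' median at 66 against 127 weeks. Those limits belong to the last and first individuals, not to whole groups, and nothing says the entry periods were separate. A third is that a large difference in rates would be hidden. At 0.15 against 0.30 per year, the n (%) table would show 45% against 78% (overlap) or 83% (split).

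**Conclusion.** The point holds as a modest one about a descriptive table. The planned figure mixes discontinuation rate with potential follow-up. That limits A+B against Part C, and the Total column. Under the stated assumptions the distortion is about 1.24 to 1.40 at an equal 0.15 per year. It is smaller at high rates or if A+B discontinues faster, and somewhat larger at very low rates. The size rests on assumed rates and on an approximate reading of the MMSE windows, so it is an illustration, not an estimate. The primary endpoint, incidence of adverse events and serious adverse events, does not depend on it.

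A secondary gap is what counts as an event. Protocol 10.1 opens its list with "A participant must discontinue study treatment for any of the following reasons", and neither the planned end of dosing nor death appears in it. SAP 4.2 mentions deaths when it describes reasons for discontinuation and withdrawal. SAP 4.6 does not say whether a subject who dies on treatment enters the calculation.

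**What to change.** Add one summary of treatment discontinuation in the whole safety population, by Table 6 group:

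- Censor subjects who reach the planned end of dosing at their last dose, and state that planned end is not discontinuation.
- State how death on treatment is counted: as a competing event in a cumulative-incidence summary, or combined with discontinuation in a Kaplan-Meier summary.
- Report the proportion discontinued at Weeks 52, 104 and 152, which every participant is planned to have the opportunity to reach.
- Keep the existing table, labelled as a description of discontinuers.
- Note that the summary removes the follow-up artefact only, and that differences in dose history, washout and disease stage between A+B and Part C remain.

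The cost is one or two SAP sentences and one extra table or figure, from dosing and death dates already collected.

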4.7. Concomitant Medications and Non-Drug Treatments/Procedures

Concomitant medications will be coded using the World Health Organization (WHO) dictionary WHODRUG (March 2024) and concomitant non-drug treatments/procedures using the Medical Dictionary for Regulatory Activities (MedDRA) version 27.0 or later.

Medications and non-drug treatments are considered concomitant if they are taken during study 233AS102. This includes medications/treatment/procedures that were started prior to the date and time of first dose of study drug if their use continued on or after the date and time of first dosing. If the start date is available but start time is missing and the medications/treatment/procedure start date is the same as the first dose date, the medications/treatment/procedure will be considered concomitant. Similarly, if the stop date is available but stop time is missing and the medications/treatment/procedure stop date is the same as the first dose date, the medications/treatment/procedure will also be considered concomitant. Medications/treatment/procedures with missing start or stop dates and times, will also be considered as concomitant in the following situations:

- If both the start and stop dates and times of a medication/treatment/procedure are missing;
- If the start date and time of a medication/treatment/procedure is missing and the stop date and time of the medication/therapy occurred on or after the date and time of first dose of study drug;
- If the start date and time of a medication/treatment/procedure therapy occurred prior to the date and time of first dose of study drug and the stop date and time of the medication/treatment/procedure is missing and the medication/treatment/procedure is listed as ongoing;

In a rare situation where the start date and time of a medication/treatment/procedure occurred prior to the date and time of first dose of study drug and both the stop date and time of the

medication/treatment/procedure is missing and the medications/treatment/procedure is not listed as ongoing, then the medication/treatment/procedure will also be considered as concomitant.

For medications/treatment/procedures with a partial start date, the year/month will be compared to that of the first dosing date to determine whether the medications/treatment/procedure is concomitant.

The number and percentage of subjects taking any concomitant medications will be summarized by study group for the safety population. The number and percentage of subjects taking any concomitant non-drug treatments will also be summarized by study group for the safety population. All medications/treatment/procedures will also be listed.

A listing of any changes to rilzuole or edaravone use during the study will be presented.

If there are a sufficient number of tests or treatments reported with indication of COVID-19, a separate summary of these will be provided. This will include a summary of the number and percentage of subjects with COVID-19 diagnostic tests with the following recorded verbatim terms (these will be coded using MedDRA dictionary):

“COVID-19 Diagnostic Test Result Positive”

“COVID-19 Diagnostic Test Result Negative”

“COVID-19 Diagnostic Test Result Pending”

“COVID-19 Diagnostic Test Result Inconclusive”

and the number and percentage of subjects with COVID-19 antibody tests with the following recorded verbatim terms (these will be coded using MedDRA dictionary):

“COVID-19 Antibody Test Result Positive”

“COVID-19 Antibody Test Result Negative”

“COVID-19 Antibody Test Result Pending”

“COVID-19 Antibody Test Result Inconclusive”

If there are very few COVID-19 tests or treatments the summary will not be presented but a listing of these will be provided.

Concomitant medications will also be reviewed by a medical reviewer prior to the final database lock to determine disallowed medications according to the protocol. These will be summarized separately.

